14.12.7. Efficacy Figures

Efficacy: Figures					
No.	Population	IDSL / Example Shell	Title	Programming Notes	Deliverable [Priority]
Co-Primary Endpoints					
2.1.	ITT	SHELL	Figure of Change from Baseline Total Endoscopic Nasal Polyps Score (Centrally Read) at Week 52	Show percentages in each category Programming Note: dataset with assigned values for subjects with surgery/missing data	SAC [1]
2.2.	ITT	SHELL	Figure of Median Change from Baseline Total Endoscopic Nasal Polyps Score (Centrally Read) by Visit	Median and 95%CI Footnote: Includes data reported up to Week 52	SAC [1]
2.3.	ITT	SHELL	Figure of Change from Baseline Total Endoscopic Nasal Polyps Score (Centrally Read) at Week 52: Cumulative Distribution Function	Programming Note: dataset with assigned values for subjects with surgery/missing data	SAC [2]

CONFIDENTIAL

205687

Efficacy: Figures					
No.	Population	IDSL / Example Shell	Title	Programming Notes	Deliverable [Priority]
2.4.	ITT	SHELL	Figure of Median Change from Baseline Total Endoscopic Nasal Polyps Score (Centrally Read) at Week 52: Primary and Sensitivity Analyses	Include primary and sensitivity analyses	SAC [2]
2.5.	ITT	SHELL	Figure of Change from Baseline Nasal Obstruction VAS Score (Week 49-52)	Show percentages in each category Programming Note: dataset with assigned values for subjects with surgery/missing data	SAC [1]
2.6.	ITT	SHELL	Figure of Median Change from Baseline Nasal Obstruction VAS Score in each 4-Weekly Period	Median and 95%CI Footnote: Includes data reported up to Week 52	SAC [1]
2.7.	ITT	SHELL	Figure of Median Change from Baseline Nasal Obstruction VAS Score (Week 49-52): Primary and Sensitivity Analyses	Include primary and sensitivity analyses	SAC [2]
Secondary Endpoints					
2.8.	ITT	SHELL	Kaplan-Meier Time to First Nasal Surgery	Footnote: Includes data reported up to Week 52	SAC [1]
2.9.	ITT	SHELL	Sensitivity Time to First Nasal Surgery: Tipping Point	Heat Map Footnote: Includes data reported up to Week 52	SAC [2]
2.10.	ITT	SHELL	Sensitivity Time to First Nasal Surgery: Tipping Point – MAR Assumption for Placebo	2-dimensional Footnote: Includes data reported up to Week 52	SAC [2]
2.11.	ITT	SHELL	Figure of Median Change from Baseline Overall VAS Score in Each 4-Weekly Period	Median and 95%CI Footnote: Includes data reported up to Week 52	SAC [1]
2.12.	ITT	SHELL	Figure of Median Change from Baseline SNOT-22 by Visit	Median and 95%CI Footnote: Includes data reported up to Week 52	SAC [1]

CONFIDENTIAL

205687

Efficacy: Figures					
No.	Population	IDSL / Example Shell	Title	Programming Notes	Deliverable [Priority]
2.13.	ITT	SHELL	Figure of Median Change from Baseline Composite VAS Score - Nasal Symptoms in each 4-Weekly Period	Median and 95%CI Footnote: Includes data reported up to Week 52	SAC [1]
2.14.	ITT	SHELL	Figure of Median Change from Baseline Loss of Smell VAS Score in each 4-Weekly Period	Median and 95%CI Footnote: Includes data reported up to Week 52	SAC [1]
Other Endpoints					
2.15.	ITT	SHELL	Figure of Total Endoscopic Nasal Polyps Score (Centrally Read) Responders by Visit	OR and 95%CI Footnote: Includes data reported up to Week 52	SAC [2]
2.16.	ITT	SHELL	Figure of University of Pennsylvania Smell Identification Test (UPSIT) Change from Baseline by Visit	Median and 95%CI Footnote: Includes data reported up to Week 52	SAC [2]
2.17.	ITT	SHELL	Figure of SNOT-22 Responders by Visit	OR and 95%CI Footnote: Includes data reported up to Week 52	SAC [2]
2.18.	ITT	SHELL	Kaplan-Meier Time to First Inclusion on Waiting List for Nasal Polyps Surgery	Footnote: Includes data reported up to Week 52	SAC [2]
2.19.	ITT	SHELL	Kaplan-Meier Time to First Course of Systemic Steroids	Footnote: Includes data reported up to Week 52	SAC [2]
2.20.	ITT	SHELL	Kaplan-Meier Time to First Nasal Surgery or Course of Systemic Steroids	Footnote: Includes data reported up to Week 52	SAC [2]
2.21.	ITT	SHELL	Figure of On-Treatment Blood Eosinophils Absolute Values	No reference line. Include screening/baseline geometric mean values without 95% CI. Week 4 onwards adjusted estimates from MMRM model with 95% CI.	SAC [2]

CONFIDENTIAL

205687

Efficacy: Figures					
No.	Population	IDSL / Example Shell	Title	Programming Notes	Deliverable [Priority]
2.22.	ITT	SHELL	Figure of On-Treatment Blood Eosinophils Ratio to Baseline	Reference line at 1	SAC [2]
Other Endpoints – Maintenance of Response Following Cessation of Interventional Product (Follow-Up Period After Week 52)					
2.23.	FU	SHELL	Kaplan-Meier Time to First Nasal Surgery for Subjects in the Follow-Up Period After Week 52		SAC [2]
2.24.	FU	SHELL	Kaplan-Meier Time to First Inclusion on Waiting List for Nasal Polyps Surgery for Subjects in the Follow-Up Period After Week 52		SAC [2]
2.25.	FU	SHELL	Figure of Blood Eosinophils for Subjects in the Follow-Up Period After Week 52		SAC [2]

14.12.8. Safety Tables

Safety: Tables					
No.	Population	IDSL / Example Shell	Title	Programming Notes	Deliverable [Priority]
Adverse Events (AEs)					
3.1.	Safety	AE13/SHELL	Adverse Event Overview		SAC [1]
3.2.	Safety	AE1	Summary of On-Treatment Adverse Events by System Organ Class and Preferred Term	ICH E3	SAC [1]
3.3.	Safety	AE1	Summary of Post-Treatment Adverse Events by System Organ Class and Preferred Term	Footnote: Includes data reported up to Week 52	SAC [1]
3.4.	FU	AE1	Summary of Adverse Events Reported During the Follow-Up Period After Week 52 by System Organ Class and Preferred Term		SAC [2]

CONFIDENTIAL

205687

Safety: Tables					
No.	Population	IDSL / Example Shell	Title	Programming Notes	Deliverable [Priority]
3.5.	Safety	AE3	Summary of Common ($\geq 3\%$ in Any Treatment Group) On-Treatment Adverse Events by Overall Frequency	ICH E3 $\geq 3\%$ (prior to rounding to nearest percent)	SAC [2]
3.6.	Safety	AE5a	Summary of On-Treatment Adverse Events by System Organ Class and Maximum Severity	Add a Total column across all severities	SAC [2]
3.7.	Safety	AE1	Summary of Drug-Related On-Treatment Adverse Events by System Organ Class and Preferred Term	ICH E3	SAC [2]
3.8.	Safety	AE5a	Summary of Drug Related On-Treatment Adverse Events by System Organ Class and Maximum Severity	Add a Total column across all severities	SAC [2]
3.9.	Safety	AE15	Summary of Common ($\geq 3\%$ In Any Treatment Group) Non-Serious On-Treatment Adverse Events by System Organ Class and Preferred Term (Number of Subjects and Occurrences)	FDAAA, EudraCT $\geq 3\%$ (prior to rounding to nearest percent)	SAC [2]
3.10.	Safety	AE1	Summary of On-Treatment Adverse Events by Highest Post-Baseline Anti-Drug Antibody Result	Add in row with n in each ADA result category. Footnote: Highest Post-Baseline Anti-Drug Antibody result excluding data from no-treatment follow-up period.	SAC [2]
3.11.	Safety	AE1	Summary of Post-Treatment Adverse Events by Highest Post-Baseline Anti-Drug Antibody Result	Add in row with n in each ADA result category. Footnote: Highest Post-Baseline Anti-Drug Antibody result excluding data from no-treatment follow-up period. Footnote: Includes data reported up to Week 52	SAC [2]
3.12.	Safety	AE1	Summary of Adverse Events Leading to Permanent Discontinuation of Study Treatment by System Organ Class	IDSL; Footnote: Includes data reported up to Week 52	SAC [2]
3.13.	Safety	AE1	Summary of Adverse Events Leading to Withdrawal from Study by System Organ Class	IDSL; Footnote: Includes data reported up to Week 52	SAC [2]

CONFIDENTIAL

205687

Safety: Tables					
No.	Population	IDSL / Example Shell	Title	Programming Notes	Deliverable [Priority]
3.14.	Safety	AE1	Summary of Adverse Events Reported on Day of Dosing by System Organ Class	Footnote: Includes data reported up to Week 52	SAC [2]
Serious and Other Significant Adverse Events					
3.15.	Safety	AE3	Summary of Fatal Serious Adverse Events		SAC [1]
3.16.	Safety	AE3	Summary of Fatal Drug-Related Serious Adverse Events		SAC [2]
3.17.	Safety	AE1	Summary of Non-Fatal Serious Adverse Events by System Organ Class	Include on-treatment and post-treatment	SAC [2]
3.18.	Safety	AE1	Summary of Non-Fatal Serious On-Treatment Adverse Events by System Organ Class		SAC [1]
3.19.	Safety	AE1	Summary of Non-Fatal Serious Post-Treatment Adverse Events by System Organ Class	Footnote: Includes data reported up to Week 52	SAC [2]
3.20.	Safety	AE1	Summary of Serious Adverse Events by System Organ Class	Include on-treatment and post-treatment	SAC [1]
3.21.	Safety	AE1	Summary of Serious On-Treatment Adverse Events by System Organ Class		SAC [2]
3.22.	Safety	AE1	Summary of Serious Post-Treatment Adverse Events by System Organ Class	Footnote: Includes data reported up to Week 52	SAC [2]
3.23.	FU	AE1	Summary of Serious Adverse Events Reported During the Follow-Up Period After Week 52 by System Organ Class		SAC [2]
3.24.	Safety	AE1	Summary of Serious Drug-Related On-Treatment Adverse Events by System Organ Class		SAC [2]
3.25.	Safety	AE1	Summary of Pre-Treatment Serious Adverse Events by System Organ Class		SAC [2]
3.26.	Safety	AE16	Summary of Serious Adverse Events by System Organ Class and Preferred Term (Number of Subjects and Occurrences)	FDAAA, EudraCT	SAC [2]

CONFIDENTIAL

205687

Safety: Tables					
No.	Population	IDSL / Example Shell	Title	Programming Notes	Deliverable [Priority]
3.27.	Safety	SHELL	Summary of Deaths	Includes all deaths separating those reported in no-treatment follow-up	SAC [2]
Adverse Events of Special Interest					
3.28.	Safety	SHELL	Summary of On-Treatment Serious AEs and AEs of Special Interest: Incidence, Relative Risk and Risk Difference (Placebo vs 100mg SC)		SAC [2]
3.29.	Safety	AE1	Summary of On-Treatment Adverse Events of Special Interest: Systemic Reactions Reported by the Investigator as Meeting the Criteria for Anaphylaxis		SAC [2]
3.30.	Safety	AE1	Summary of On-Treatment Adverse Events of Special Interest: Events Reported by the Investigator as Systemic Reactions – Allergic (Type I Hypersensitivity) and Other Reactions		SAC [2]
3.31.	Safety	AE1	Summary of On-Treatment Adverse Events of Special Interest: Events Reported by the Investigator as Systemic Reactions – Allergic (Type I Hypersensitivity)		SAC [2]
3.32.	Safety	AE1	Summary of On-Treatment Adverse Events of Special Interest: Events Reported by the Investigator as Systemic Reactions – Other Reactions		SAC [2]
3.33.	Safety	AE1	Summary of On-Treatment Adverse Events of Special Interest: Events Reported by the Investigator as Local Injection Site Reactions		SAC [2]
3.34.	Safety	AE1	Summary of On-Treatment Adverse Events of Special Interest: Serious Cardiac, Vascular and Thromboembolic Events		SAC [2]
3.35.	Safety	AE1	Summary of On-Treatment Adverse Events of Special Interest: Serious Ischemic Events		SAC [2]

CONFIDENTIAL

205687

Safety: Tables					
No.	Population	IDSL / Example Shell	Title	Programming Notes	Deliverable [Priority]
3.36.	Safety	AE1	Summary of On-Treatment Adverse Events of Special Interest: Malignancies		SAC [2]
3.37.	Safety	AE1	Summary of On-Treatment Adverse Events of Special Interest: Potential Opportunistic Infections		SAC [2]
3.38.	Safety	SHELL	Summary Profile of On-Treatment Adverse Events of Special Interest: Systemic Reactions Reported by the Investigator as Meeting the Criteria for Anaphylaxis		SAC [2]
3.39.	Safety	SHELL	Summary Profile of On-Treatment Adverse Events of Special Interest: Events Reported by the Investigator as Systemic Reactions – Allergic (Type I Hypersensitivity) and Other Reactions		SAC [2]
3.40.	Safety	SHELL	Summary Profile of On-Treatment Adverse Events of Special Interest: Events Reported by the Investigator as Systemic Reactions – Allergic (Type I Hypersensitivity)		SAC [2]
3.41.	Safety	SHELL	Summary Profile of On-Treatment Adverse Events of Special Interest: Events Reported by the Investigator as Systemic Reactions –Other Reactions		SAC [2]
3.42.	Safety	SHELL	Summary Profile of On-Treatment Adverse Events of Special Interest: Events Reported by the Investigator as Local Injection Site Reactions		SAC [2]
3.43.	Safety	SHELL	Summary Profile of On-Treatment Adverse Events of Special Interest: Serious Cardiac, Vascular and Thromboembolic Events		SAC [2]
3.44.	Safety	SHELL	Summary Profile of On-Treatment Adverse Events of Special Interest: Serious Ischemic Events		SAC [2]
3.45.	Safety	SHELL	Summary Profile of On-Treatment Adverse Events of Special Interest: Malignancies		SAC [2]

CONFIDENTIAL

205687

Safety: Tables					
No.	Population	IDSL / Example Shell	Title	Programming Notes	Deliverable [Priority]
3.46.	Safety	SHELL	Summary Profile of On-Treatment Adverse Events of Special Interest: Potential Opportunistic Infections		SAC [2]
Laboratory: Chemistry					
3.47.	Safety	LB1	Summary of On-Treatment Chemistry Changes from Baseline	ICH E3 Includes Baseline values	SAC [2]
3.48.	Safety	LB3	Summary of On-Treatment Chemistry Shifts from Baseline Relative to Normal Range	ICH E3 Include Any Time Post Baseline Add footnotes: Note: Any Time Post Baseline – Includes scheduled and any unscheduled assessments Subjects may be counted in more than one category.	SAC [2]
3.49.	Safety	LB3	Summary of On-Treatment Chemistry Shifts from Baseline Relative to PCI Criteria	ICH E3 Include Any Time Post Baseline Add footnotes: Note: Any Time Post Baseline – Includes scheduled and any unscheduled assessments Subjects may be counted in more than one category.	SAC [2]
Laboratory: Hematology					
3.50.	Safety	LB1	Summary of On-Treatment Haematology Changes from Baseline	ICH E3 Includes Baseline values	SAC [2]

CONFIDENTIAL

205687

Safety: Tables					
No.	Population	IDSL / Example Shell	Title	Programming Notes	Deliverable [Priority]
3.51.	Safety	LB3	Summary of On-Treatment Haematology Shifts from Baseline Relative to Normal Range	ICH E3 Include Any Time Post Baseline Add footnotes: Note: Any Time Post Baseline – Includes scheduled and any unscheduled assessments Subjects may be counted in more than one category.	SAC [2]
3.52.	Safety	LB3	Summary of On-Treatment Haematology Shifts from Baseline Relative to PCI Criteria	ICH E3 Include Any Time Post Baseline Add footnotes: Note: Any Time Post Baseline – Includes scheduled and any unscheduled assessments Subjects may be counted in more than one category.	SAC [2]
Laboratory: Urinalysis					
3.53.	Safety	UR1	Summary of Worst Case On-Treatment Urinalysis Results Post-Baseline Relative to Baseline	ICH E3	SAC [2]
Laboratory: Hepatobiliary (Liver)					
3.54.	Safety	LIVER1	Summary of Liver Monitoring/Stopping Event Reporting	IDSL	SAC [2]
3.55.	Safety	LIVER10	Summary of Hepatobiliary Laboratory Abnormalities	IDSL	SAC [2]
ECG					
3.56.	Safety	EG1	Summary of ECG Findings	IDSL	SAC [2]
3.57.	Safety	EG2	Summary of Change from Baseline in ECG Values by Visit	IDSL	SAC [2]

CONFIDENTIAL

205687

Safety: Tables					
No.	Population	IDSL / Example Shell	Title	Programming Notes	Deliverable [Priority]
3.58.	Safety	EG10	Summary of Maximum QTc Values Post-Baseline Relative to Baseline by Category	IDSL	SAC [2]
3.59.	Safety	EG11	Summary of Maximum Increase in QTc Values Post-Baseline Relative to Baseline by Category	IDSL	SAC [2]
Vital Signs					
3.60.	Safety	VS1	Summary Vital Signs		SAC [2]
3.61.	Safety	VS1	Summary of Change from Baseline in Vital Signs	ICH E3	SAC [2]
Immunogenicity					
3.62.	Safety	SHELL	Summary of Binding Anti Drug Antibody Assay: Highest Confirmatory Result	Footnote: Includes data reported up to Week 52	SAC [2]
3.63.	Safety	SHELL	Summary of Binding Anti Drug Antibody Assay: Highest Treatment Emergent Confirmatory Result	Footnote: Includes data reported up to Week 52	SAC [2]
3.64.	Safety	SHELL	Summary of Neutralising Antibody Assay: Highest Result	Footnote: Includes data reported up to Week 52	SAC [2]
3.65.	FU	SHELL	Summary of Binding Anti Drug Antibody Assay: Highest Confirmatory Result for Subjects in the Follow-up Period After Week 52	Footnote: Includes all available data	SAC [2]
3.66.	FU	SHELL	Summary of Binding Anti Drug Antibody Assay: Highest Treatment Emergent Confirmatory Results for Subjects in the Follow-up Period After Week 52	Footnote: Includes all available data	SAC [2]
3.67.	FU	SHELL	Summary of Neutralising Antibody Assay: Highest Result for Subjects in the Follow-up Period After Week 52	Footnote: Includes all available data	SAC [2]
3.68.	Safety	SHELL	Summary of On-Treatment Blood Eosinophils (GI/L) by Anti Drug Antibody Status		SAC [2]

CONFIDENTIAL

205687

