### 3.2.1. Risk Assessment

The following section outlines the key risks, risk assessment and mitigation strategy for this protocol based on mepolizumab lyophilised formulation. The safety profile of the mepolizumab liquid formulation is anticipated to be similar to the lyophilised formulation.

Potential Risk of Clinical Significance	Summary of Data/Rationale for Risk	Mitigation Strategy
Investigational Product (IP)		
Risk of Systemic Reactions including allergic reactions	
Biopharmaceutical products - may elicit systemic (e.g. hypersensitivity) reactions.
 
In the placebo controlled severe asthma (PCSA) studies both acute and delayed systemic reactions including hypersensitivity have been reported following administration of mepolizumab with incidence rates similar between mepolizumab and placebo-treated participants:
 
 
• 54/915 participants or 6% in the mepolizumab [all doses combined] group
 
• 7/263 participants or 3% in the mepolizumab 100 mg SC group
 
• 12/344 participants or 3% in the mepolizumab 75 mg IV group
 
• 20/412 participants or 5% in the placebo group.
 
 
The most common symptoms reported with any systemic reaction included headache, rash, pruritus, fatigue, and dizziness. While rare, serious systemic reactions have been reported. Events of anaphylaxis attributed to mepolizumab have been reported post-marketing.
 
Systemic reactions reported to date across the mepolizumab programme are summarized in the IB “Adverse Events of Special Interest” section; see also
	
Daily monitoring of serious adverse events (SAEs) by medical monitor; regular systematic review of adverse event (AE)/SAE data from ongoing studies by the GSK study team and/or safety review team.
 
Customised AE and SAE case report form (CRF) utilised for targeted collection of information for systemic reaction adverse events.
 
Use of Joint NIAID/FAAN 2nd Symposium on Anaphylaxis to collect data on reports of anaphylaxis (see Appendix 11: Anaphylaxis Criteria).
 
Participants are monitored in clinic for at least 1 hour following administration of IP for the first 3 doses then per institutional guidelines.

Potential Risk of Clinical Significance	Summary of Data/Rationale for Risk	Mitigation Strategy

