8. SAFETY ANALYSES

The safety analyses will be based on the Safety population. Unless otherwise specified data reported as part of the no-treatment follow-up will not be included in summaries of on-treatment data or post-treatment data. Data reported during the no-treatment follow-up will be summarised separately.

Summaries of adverse events (AEs), serious adverse events (SAEs) and other significant AEs will be based on GSK Core Data Standards. The details of the planned displays are provided in [Appendix 12: List of Data Displays](#).

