8.1. Adverse Events Analyses

8.2. Adverse Events of Special Interest Analyses

Adverse events of special interest (AESIs) are adverse events which are to be closely monitored as the development of mepolizumab progresses.

Systemic reactions are AESIs which are collected via targeted eCRF and further categorised by the investigator as either an allergic (type I hypersensitivity) or other systemic reaction. These events are required to be assessed against Sampson's diagnostic criteria for anaphylaxis. Local injection site reactions are also collected via targeted eCRF within the study.

AESIs of potential opportunistic infections, malignancies, serious cardiac, vascular and thromboembolic (CVT) events and serious ischemic events will be identified from a list

of relevant preferred terms maintained within a project level reference dataset created based on the MedDRA dictionary available at the time of source data lock for this study. Further details of how relevant preferred terms are identified for the AESIs are given in the Program Safety Analysis Plan (PSAP).

Separate summary tables showing the number and percent of participants with each type of AESI, broken down by preferred term will be created. These summaries will be reported as part of the standard AE/SAE tables for the AESIs of infections, serious infections, neoplasms, cardiac disorders and serious cardiac disorders. The relative risk of each AESI between mepolizumab and placebo will be presented with 95% confidence intervals.

For each AESI a profile summary table will be produced containing information on event characteristics including, but not be limited to, the number of participants with the AESI, the number of occurrences of the AESI, the number of participants with a serious event or a drug related event, summaries by maximum severity and separately by outcome.

Separate listings will be provided of participants with systemic reactions identified by the investigator as meeting the criteria for anaphylaxis, systemic reactions categorised as allergic (type I hypersensitivity), systemic reactions categorised as other, and all other AESIs.

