14.12.9. Safety Figures

Safety: Figures					
No.	Population	IDSL / Example Shell	Title	Programming Notes	Deliverable [Priority]
Adverse Events					
3.1.	Safety	AE10	Common (>=3% In Any Treatment Group) On-Treatment Adverse Events and Relative Risk	IDSL	SAC [2]
3.2.	Safety	SHELL	On-treatment Serious Adverse Events and Adverse Events of Special Interest (Placebo vs Mepolizumab 100mg SC)	Provide relative risk with 95% CI	SAC [2]
Laboratory					
3.3.	Safety	LIVER9	Scatter Plot of Maximum ALT vs. Maximum Total Bilirubin	IDSL	SAC [2]

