36.	Safety	AE8	Listing of On-Treatment Adverse Events of Special Interest: Events Reported by the Investigator as Systemic Reactions – Allergic (Type I Hypersensitivity)	add Phase(on/post-trt) add number of doses taken prior to the event and symptoms related to the event	SAC [2]
37.	Safety	AE8	Listing of On-Treatment Adverse Events of Special Interest: Events Reported by the Investigator as Systemic Reactions – Other Reactions	add Phase(on/post-trt) add number of doses taken prior to the event and symptoms related to the event	SAC [2]
38.	Safety	AE8	Listing of On-Treatment Adverse Events of Special Interest: Events Reported by the Investigator as Local Injection Site Reactions	add Phase(on/post-trt) add number of doses taken prior to the event and symptoms related to the event	SAC [2]
39.	Safety	AE8	Listing of On-Treatment Adverse Events of Special Interest: Serious Cardiac, Vascular and Thromboembolic Events	add Phase(on/post-trt)	SAC [2]

CONFIDENTIAL

205687

ICH and Other Listings					
No.	Population	IDSL / Example Shell	Title	Programming Notes	Deliverable [Priority]
40.	Safety	AE8	Listing of On-Treatment Adverse Events of Special Interest: Serious Ischemic Events	add Phase(on/post-trt)	SAC [2]
41.	Safety	AE8	Listing of On-Treatment Adverse Events of Special Interest: Malignancies	add Phase(on/post-trt)	SAC [2]
42.	Safety	AE8	Listing of On-Treatment Adverse Events of Special Interest: Potential Opportunistic Infections	add Phase(on/post-trt)	SAC [2]
Hepatobiliary (Liver)					
43.	Safety	MH2	Listing of Medical Conditions for Subjects with Liver Stopping Events	IDSL	SAC [2]
44.	Safety	LIVER13	Listing of Subjects Meeting Hepatobiliary Laboratory Criteria Post-Baseline		SAC [2]
45.	Safety	LIVER5	Listing of Liver Monitoring/Stopping Event Reporting		SAC [2]
46.	Safety	SU2	Listing of Substance Use for Subjects with Liver Stopping Events	IDSL	SAC [2]
All Laboratory					
47.	Safety	LB5	Listing of Chemistry Data for Subjects with Any Value of Potential Clinical Importance	ICH E3	SAC [2]
48.	Safety	LB5	Listing of Haematology Data for Subjects with Any Value of Potential Clinical Importance	ICH E3	SAC [2]
49.	Safety	LB14	Listing of Laboratory Data with Character Results	ICH E3	SAC [2]
50.	Safety	UR2A/UR2B	Listing of Urinalysis Data for Subjects with Any Value of Potential Clinical Importance	ICH E3	SAC [2]
ECG					

CONFIDENTIAL

205687

ICH and Other Listings					
No.	Population	IDSL / Example Shell	Title	Programming Notes	Deliverable [Priority]

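### Every AESI-specific table and relative risk stops at last dose + 28 days; a supplementary summary that counts later events is missing

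*SAP*

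**What the plan says.** All references are to the current analysis plan (RAP Amendment 1).

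- SAP 8.2 plans, for each AESI type, the number and percent of participants, and states that "The relative risk of each AESI between mepolizumab and placebo will be presented with 95% confidence intervals". It gives no time window.
- The window comes from the display list in SAP 14.12.8 and 14.12.9. Table 3.28 is titled "Summary of On-Treatment Serious AEs and AEs of Special Interest: Incidence, Relative Risk and Risk Difference (Placebo vs 100mg SC". Tables 3.29-3.37 (by AESI type) and 3.38-3.46 (profiles) carry the same label, for example "Summary of On-Treatment Adverse Events of Special Interest: Malignancies" (Table 3.36) and "Summary Profile of On-Treatment Adverse Events of Special Interest: Potential Opportunistic Infections" (Table 3.46). So does the relative-risk display, Figure 3.2.
- SAP 14.4.1.3 ends the on-treatment phase for adverse events at the stop date of study drug plus 28 days. Events with a missing start date, or where the drug stop date is missing, count as on-treatment.
- Protocol 9.3.1 collects adverse events to the end of the study. Protocol 8.2.1 asks that early discontinuers be followed where possible. Up to the first 200 randomised participants are followed to Week 76.
- SAP 8 says of that last period: "Data reported during the no-treatment follow-up will be summarised separately". Tables 3.4 and 3.23 do this for AEs and SAEs. No table does it for AESIs.
- The AESI listings (35-42 in SAP 14.12.15) are titled in the same way, for example "Listing of On-Treatment Adverse Events of Special Interest: Malignancies". Their programming notes nevertheless ask for a phase column that separates on-treatment from post-treatment events.

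**The concern.** Malignancy, opportunistic infection and serious cardiovascular events can plausibly be diagnosed more than four weeks after a last injection. Protocol 5.5 equates about three months with three mepolizumab half-lives, so 28 days is roughly one half-life. It also reports blood eosinophils returning to baseline only after about three months. That observation followed 750 mg IV, so it may not carry over exactly to 100 mg SC, but it shows that the drug's effect need not end at the cut-off.

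A participant who stops drug and is diagnosed five weeks later is recorded by the trial but does not enter the AESI incidence or relative risk. AESIs are rare, so one such event could visibly move a relative risk. If the arms stopped drug at different rates, their counting windows would also differ.

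**Working it through.** **Inputs.** Last dose Day 337 (Week 48), Week 52 visit Day 365 and Week 76 visit Day 533 (schedule of activities). 400 planned participants, up to 200 in follow-up. The SAP 14.6.3 exposure formula is (stop date − start date + 29)/365.25.

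**The plan's own figure.** Protocol 7 gives a drug-free period of up to 28 weeks. 533 − 337 = 196 days = 28.0 weeks, which agrees.

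**Completers before Week 52.** The on-treatment phase ends on Day 337 + 28 = Day 365, the nominal Week 52 visit. Nothing is lost apart from a few days when that visit falls late within its ±7-day window.

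**Follow-up after Week 52.** Days 366-533 are 168 days per participant.
- 200 × 168/365.25 = 92.0 participant-years. This is a maximum.
- With 150 or 100 in follow-up it is 69.0 or 46.0.

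**Time to Week 52 in all participants.** 400 × (337 − 1 + 29)/365.25 = 399.7 participant-years if everyone is observed to Day 365.

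**Early stoppers before Week 52.** The documents give no discontinuation rate. Assume that 10-20% stop, with last dose on average at Day 168, and that all are followed to Day 365.
- Time outside the window: (365 − 168 − 28)/365.25 = 169/365.25 = 0.463 year each.
- 40 participants: 18.5 participant-years, and 18.5/399.7 = 4.6%.
- 80 participants: 37.0 participant-years, and 37.0/399.7 = 9.3%.
- Using the scheduled Week 24 dose day (Day 169) instead gives 18.4 and 36.8.

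**In events.** At an assumed constant 1 AESI per 100 participant-years, 18.5-37.0 years correspond to 0.19-0.37 expected events before Week 52 across both arms. The 92 follow-up years correspond to at most 0.92.

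**Where a later event does appear.**

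| Display | Covers later events? | AESI grouping or relative risk? |
|---|---|---|
| 3.28-3.46, Figure 3.2 | No | Yes |
| 3.3, 3.19, 3.22 (post-treatment) | Yes, to Week 52 | No |
| 3.17, 3.20 (SAEs, on- plus post-treatment) | Yes, serious events | No |
| 3.4, 3.23 (follow-up) | Yes, after Week 52 | No |
| Listings 16 and 18 | Yes | No |
| Listings 35-42 | Unclear: title and note conflict | Grouping only |

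**The case against.** The case for the plan as written is substantial.

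- **The window fits the endpoint.** Protocol 4 and SAP 2.1 define the safety endpoint as events reported during the treatment period. An on-treatment main display follows from that. This stands.
- **SAP 8 is kept.** Its sentence on separate summaries does not promise AESI grouping, and Tables 3.4 and 3.23 satisfy it. A reader might infer a breach, but there is none.
- **Nothing leaves the report.** SAP 8.2 routes infections, serious infections, neoplasms, cardiac disorders and serious cardiac disorders to the standard AE and SAE tables, which have post-treatment and follow-up versions. The thromboembolic and ischaemic AESIs are serious by definition, so those up to Week 52 also fall in Table 3.20. Listing 16 shows all AEs with phase, and Listing 18 is split by phase. A reader might infer that later events vanish, but the documents show otherwise. What they lose is the AESI term list and the relative risk.
- **Delayed systemic reactions.** Protocol 3.2.1 says that "both acute and delayed systemic reactions including hypersensitivity have been reported following administration of mepolizumab". A reader might infer that such reactions fall past the cut-off. No latency is given, dosing is every 28 days, and no document places these reactions beyond 28 days. They do not support the point, and nor do local injection site reactions.
- **Size.** Adding follow-up and early stoppers gives (92.0 + 18.5)/491.7 = 22% to (92.0 + 37.0)/491.7 = 26% of collected time. It is tempting to read this as the share missing from the relative risk. Most of it is post-Week-52 time, which belongs in a separate follow-up table and would not enter a relative risk to Week 52. For that comparison the figure is 5-9%.

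After all this, one gap remains. No planned display counts a later event as an AESI, except possibly the listings, whose titles and notes disagree.

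**Conclusion.** The point holds as a missing supplementary analysis. The on-treatment AESI tables can stay as the main display. The plan lacks AESI incidence and relative risk that include events after last dose + 28 days, although the data are collected, SAP 8.2 sets no such limit, and the SAP already pools on- and post-treatment SAEs in Tables 3.17 and 3.20.

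The size is modest: about 18.5-37 participant-years before Week 52, if 10-20% stop mid-study and all are followed, and at most 92 afterwards. The second figure assumes that the full 200 enter and complete follow-up. Bias in the relative risk would need the arms to stop drug at different rates, for which the documents offer no evidence. The conflict between the titles and notes of Listings 35-42 depends on no assumption and should be corrected in any case.

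**What to change.** 1. Keep all on-treatment AESI displays.
2. Add a version of Table 3.28, Figure 3.2 and Tables 3.34-3.37 for all events from first dose to Week 52, on- plus post-treatment, on the model of Table 3.20.
3. Add one AESI table for the follow-up population, on the model of Tables 3.4 and 3.23.
4. Remove the on-treatment label from the titles of Listings 35-42 so that they agree with their phase column.

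The cost is an edit to the SAP display list and reruns of existing programs without the phase filter. No new data are needed, no confirmatory test is affected, and clinical management does not change. The downside is a few more tables and a window that mixes time on and off drug, which the retained on-treatment tables keep apart.
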